### **Recorded Temperature – Overall Summary**

A table summarizing the percentage of subjects experiencing fever will be provided using the temperatures recorded by the subject during the 8-day period post first, second and first or second vaccination. A subject aged <60 years will be said to have fever at a given day if his/her recorded temperature for that day is  $\geq 38.0^{\circ}\text{C}$ .

A subject aged  $\geq 60$  years will be said to have fever at a given day if his/her recorded temperature for that day  $\geq 37.3^{\circ}\text{C}$ .

### **Local and Systemic Reactogenicity Events –Summaries by Severity (Grade)**

The following grading scale was used by the subject to rate how intense or annoying each symptom was: 1-mild, 2-moderate, 3-severe.

All the above summaries will be provided by severity (or grade) also.

The severity of an event reported within a period (8-day period post first vaccination, 8-day period post second vaccination) will be the maximum severity recorded for the event during the period.

In the case that a subject has more than one event with different levels of severity over the 2 periods considered (first and second vaccination), then the maximum severity level will be used in the analysis over the 2 periods.

The severity, which is missing for an event, will remain missing in the analysis.

### **Recorded Temperature by Severity – Overall Summary**

A table summarizing the grading of the temperatures will also be provided using the temperatures recorded by the subject during the 8-day post first, second and first or second vaccination. Temperature will be graded as in Table 3.

The severity, which is missing for an event, will remain missing in the analysis.

The percentage of subjects with temperature overall and by vaccination will be compared between the groups using the chi-square test. Within-group comparison between the percentage of subjects with temperature after first and second vaccination will be performed using Mc Nemar test.

Table 3: Quantitative Systemic Reactogenicity Grading

Systemic (Quantitative)	Mild (Grade 1)	Moderate (Grade 2)	Severe (Grade 3)
(Age <60 years) Fever - oral	38.0°C – 38.4°C	38.5°C – 38.9°C	>38.9°C
(Age ≥60 years) Fever - oral	37.3.0°C – 37.7°C	37.8°C – 38.2°C	>38.2°C

### Unsolicited Adverse Events

All unsolicited AEs will be coded by the Medical Dictionary for Regulatory Activities (MedDRA) version 21.0.

Unsolicited AEs – which do not meet SAE criteria, nor ILI, AESI or NOCI definition – were to be reported until ~22 days post each study vaccination. The cut-off of 22 days post each study vaccination will be used; however, tables including all unsolicited AEs started up to 30 days after Visit 4 or after discontinuation will be provided. SAEs and NOCIs reported from the time of the first study vaccination and up to 30 days after Visit 4 or after discontinuation will be included in all SAEs and NOCIs tables.

The following ordering will be used to define the maximum level for intensity, action taken, outcome, causality, or seriousness, when needed :

- Intensity: Mild < Moderate < Severe
- Causality: No (None or Unlikely) < Yes (Possible, Probable, Certain)
- Seriousness: No < Yes
- Action taken: None – Not Applicable < Drug withdrawn
- Outcome: Unknown < Recovered/resolved < Recovered/resolved with sequelae < Recovering/resolving < Not recovered/not resolved < Fatal.

The intensity, missing for an AE, will be imputed as severe. These imputed values will be used for the summary of AEs by severity, while the actual values will be presented in the data listings.

An AE, whose relationship to vaccine is missing, will be considered as related. These imputed values will be used for the summary of AEs by relationship to vaccine; the actual values will be presented in data listings.

Local and systemic reactogenicity **solicited** events will be included in the table for unsolicited adverse events with the severity provided by the investigator, which may differ from that given by the subject’s diary. Also, the relationship to vaccine for solicited events will be that recorded by the investigator.

A second set of tables for unsolicited adverse events will be generated in which the local and systemic reactogenicity events are excluded unless the event is considered serious or it is ongoing at the end of the observation period for solicited events. The first set of tables follows the guidelines of the EMA while the second set follows those of the US Food and Drug Administration.

A general summary of all AEs occurring after the first vaccination will show the number and percentage of subjects with

- Any AE,
- Any AE with death as outcome,
- Any severe AE,
- Any AE causally related to vaccine (Relationship to Study vaccine Possible, Probable, or Certain),
- Any serious AE,
- AE leading to vaccine withdrawal,
- Not recovered or not resolved AE,
- AE of special interest,
- New onset of chronic illness,
- New onset of serious chronic illness.

The number and percentage of subjects who experienced one or more AEs will be tabulated by group and by:

- SOC, and PT
- SOC, and PT (Severe AEs)
- SOC, and PT (AEs causally related with the vaccine)

All the above tables will be presented for the entire safety population (2 seasons) and by season as well. All the above tables will report the number of AE by group in addition of the number and percentage of subjects who experience the AE. Tables by age category will be provided also.

Tables by SOC and PT will be sorted by descending percentage of events (by SOC, and By PT within SOC) for the vaccine group. In case of same percentages, sorting will be done descending number of events. In case of same percentages and number of events, sorting will be done by alphabetical order.

### **Serious Adverse Events and NOCIs**

SAEs and NOCIs from the time of the first study vaccination (Day 0 (Visit 1)) and up to 30 days after Visit 4 or after discontinuation (Visit 4) will be described. Any SAE or NOCI occurring more than 30 days after Visit 4 or after discontinuation will not be reported in the below analyses, but will be listed.

Three set of tables will be provided reporting:

- All SAEs,
- Adverse events of special interest (AESIs) captured as SAEs will be reported separately. These include a new onset of Guillain-Barré Syndrome (GBS), Bell's Palsy, encephalitis / myelitis, optic neuritis, Stevens-Johnson Syndrome, and toxic epidermal necrolysis,
- NOCIs events (serious or not).

For all tables, rules about multiple occurrences of an AE in the same subject and about missing intensity, action taken, outcome, causality, or seriousness level are identical to those described above.

A general summary of all SAEs will show by group the number and percentage of subjects with

- Any SAE,
- Any SAE with death as outcome,
- Any SAE causally related to vaccine.

The number and percentage of subjects who experienced one or more SAEs will be tabulated by group :

- SOC, and PT
- SOC, and PT (AEs causally related with the vaccine (Possible, Probable, or Certain))

Within group 95% CI for the proportion of subjects with serious SAEs will be derived using the exact method by SOC, PT.

The number and percentage of subjects who experienced one or more AESIs will be tabulated by group and:

- PT

Specific tables will be provided for NOCIs.

A general summary of all NOCIs will show the number and percentage of subjects with

- Any NOCI,
- Any NOCI with death as outcome
- Any NOCI causally related to vaccine,

The number and percentage of subjects who experience one or more NOCIs will be tabulated by group:

- SOC, and PT
- SOC, and PT (NOCIs causally related with the vaccine (Possible, Probable, or Certain))

All the above tables will be presented for the entire safety population (2 seasons) and by season as well. All the above tables will report the number of AE by group in addition of the number and percentage of subjects who experience the AE. Tables by age category will be provided also.

Tables by SOC and PT will be sorted by descending percentage of events (by SOC, and By PT within SOC) for the vaccine group. In case of same percentages, sorting will be done descending number of events. In case of same percentages and number of events, sorting will be done by alphabetical order.

Any SAE or NOCI occurring more than 30 days after Visit 4 or after discontinuation will be listed separately.

Key subject information (age/sex/race/medical history) for subjects experiencing SAEs or NOCIs will be presented in a listing together with all recorded information about the SAE or NOCI.

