3.2. Study Outcome Measures

3.2.1. Primary Outcome Measures

Safety

- Occurrence of vaccine-related SAEs from the time of the first study vaccination (M-001 or placebo) until end of first passive surveillance period
- Occurrence of NOCIs from the time of the first study vaccination (M-001 or placebo) until end of first passive surveillance period
- Occurrence of solicited injection site and systemic reactogenicity events on the day of each study vaccination through 8 days after each study vaccination (day of the vaccination inclusive)
- Occurrence of unsolicited AEs from the time of first study vaccination through 22 days after each study vaccination (day of the vaccination inclusive)
- Occurrence of all SAEs, regardless of the assessment of relatedness, from the time of receiving the first M-001 study vaccination until end of first passive surveillance period

Clinical Efficacy

- Percentage of either qRT-PCR or culture-confirmed influenza cases in the M-001 experimental group vs. placebo (during period of ≥ 15 days after the second vaccination until epidemiological levels of influenza are low as defined by the medical director) caused by any influenza A or B virus in association with a protocol defined Influenza Like Illness (ILI is defined as symptoms that include one of the respiratory symptoms (sore throat, cough, sputum production, nasal discharge or congestion, wheezing or difficult breathing) and at least one additional systemic symptom [fever (oral temperature $>37.2^{\circ}\text{C}$ for age 50-59, or $>36.7^{\circ}\text{C}$ for age 60 or more, or increased $\geq 1.3^{\circ}\text{C}$ from baseline), headache, myalgia and/or arthralgia, chills, and fatigue (tiredness for at least 12 hours)]. NP or combined nasal and throat swab will be collected from participants who meet the ILI definition within 24 hours from ILI being reported to or identified by study personnel for qRT-PCR analysis of influenza A and/or B virus. PCR confirmed samples will be further analyzed for culture confirmation.

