All serious adverse events (SAEs) and new onset of chronic medical illness (NOCIs) will be collected from Day 0 until the end of the participation in the trial by the subject.

Adverse events of special interest (AESIs) will be captured as SAEs. These include new onset of Guillain-Barré Syndrome (GBS), Bell's Palsy, encephalitis / myelitis, optic neuritis, Stevens-Johnson Syndrome, and toxic epidermal necrolysis.

Passive efficacy surveillance: Following randomization and vaccinations, subjects will be instructed to contact the site if they experience symptoms of a respiratory illness or influenza-like illness during the annual surveillance periods defined as from Day 14 after second vaccination day until 15 May of the following year.

Active efficacy surveillance will be performed from November 15th (in Season 1) or from December 1st (in Season 2) until the week of 30 March the following year, the most likely period of influenza virus circulation in the Northern Hemisphere.

The participants will be contacted by a dedicated study staff up to twice a week between approximately November 15th through March 31st.

Participants will be contacted as described above by non-site study staff to monitor for influenza-like illness (ILI).; participants identified this way as potentially having ILI will be followed up by relevant study site personnel to confirm if the participant's symptoms and signs meet study ILI definition.

ILI is NOT to be understood as condition caused specifically by influenza virus. The etiology of ILI may be very different, and only after analysis of swabs taken from subjects, the presence or absence of influenza virus in swab sample can be determined. Hence, even if it is suspected that ILI is caused by e.g. a bacteria, or by some other virus than influenza virus, such ILI remains valid reason for swab collection, also because in some cases there may be a superinfection or parallel infection with influenza virus.

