The Sponsor's Responsible Medical Director will base the decision on the following criteria:

- 1) The influenza activity level for the region/zone where the research site is located has to be evident by increased ILI and laboratory confirmed influenza detection together with e.g. outbreaks in schools, hospitals, residential institutions and/or other types of facilities occurring in less than 50% of the influenza surveillance region), based on the most updated report.
- 2) The percentage of specimens tested that are positive for influenza has to be at least 10% for the country where the site is located, based on data present in the most updated report.

If the 2 criteria are met for the region/zone where the research site is located, the site will be instructed to continue obtaining NP/nasal and throat swabs if a subject has a new influenza-like illness.

On 15 May (unless other instructions are given by the medical director), all surveillance and the swab collection procedures will end.

Any influenza A or B strain will be included in the vaccine efficacy analysis. Culture confirmation of influenza will be performed only for qRT-PCR highly positive samples.

After 30th of April, passive surveillance will continue, with subjects expected to call the research site to report the occurrence of any new respiratory illness or influenza-like illness symptoms. However, the research site will schedule the collection of the NP/ nasal and throat swab only if the Sponsor has categorized the site as requiring continued testing based

on DSMB recommendation which will be based on influenza epidemiologic data. The Sponsor's Responsible Medical Director will perform weekly assessments of the applicable influenza surveillance system to determine whether a particular research site needs to continue collecting the swabs.

ILI follow-up calls:

Any ILI must be followed up for up to 30 days following the start date or until resolved. Site personnel will follow up the participant with ILI at 10±3 days after ILI start date. Follow up information on symptoms associated with the ILI will be collected by study staff through a telephone call performed at 10±3 days (and up to 30 days) (unless collected at unscheduled site visit at relevant time point) following the illness start date.

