## 3. STUDY OUTCOME MEASURES

### 3.1 Primary Outcome Measures

#### Safety

- Occurrence of vaccine-related SAEs from the time of the first study vaccination (M-001 or placebo) until end of the passive surveillance period
- Occurrence of NOCIs from the time of the first study vaccination (M-001 or placebo) until end of the passive surveillance period
- Occurrence of solicited injection site and systemic reactogenicity events on the day of each study vaccination through 8 days after each M-001 vaccination (day of the vaccination inclusive)
- Occurrence of unsolicited AEs from the time of first study vaccination through 22 days after each M-001 vaccination (day of the vaccination inclusive)
- Occurrence of all SAEs, regardless of the assessment of relatedness, from the time of receiving the first M-001 study vaccination until end of the passive surveillance period

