#### Surveillance for respiratory illness – Flu season 2019-2020

- *Active Surveillance:* All subjects will be contacted twice a week by a call center starting on December 1st, 2019 until the week of April 30th.
- *Passive Surveillance:* All subjects will be instructed to contact their study site if they experience symptoms of a respiratory illness from September 15, 2019 to May 15, 2020.

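### The SAE, AESI and NOCI tables stop 30 days after Visit 4 or discontinuation, while the primary outcomes they report run to the end of passive surveillance

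*SAP*

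**What the plan says.** Protocol 3.2.1 and SAP 3.1 each list five primary safety outcomes. Two have short fixed windows (8 days for solicited events, 22 days for unsolicited AEs) and are not at issue. The other three are vaccine-related SAEs, NOCIs and all SAEs. The protocol gives the window as "Occurrence of vaccine-related SAEs from the time of the first study vaccination (M-001 or placebo) until end of first passive surveillance period", and the SAP does the same, for example "Occurrence of NOCIs from the time of the first study vaccination (M-001 or placebo) until end of the passive surveillance period".

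The end of passive surveillance is a calendar date. Protocol 7.3 has it run "from Day 14 after second vaccination day until 15 May of the following year", and lets the medical director give other instructions. SAP 5.1 also ends it on 15 May for season 2018-2019; for season 2019-2020 it gives the period as "from September 15, 2019 to May 15, 2020".

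SAP 4.4 sets a different end for the tables. Under unsolicited adverse events, SAEs and NOCIs reported from first vaccination and "up to 30 days after Visit 4 or after discontinuation will be included in all SAEs and NOCIs tables". The part on SAEs and NOCIs repeats the limit: "Any SAE or NOCI occurring more than 30 days after Visit 4 or after discontinuation will not be reported in the below analyses". AESIs are captured as SAEs, so the same limit reaches them. What falls later goes to a listing: "Any SAE or NOCI occurring more than 30 days after Visit 4 or after discontinuation will be listed separately".

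SAP section 11, which sets out the changes from the protocol analyses, does not mention this.

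**The concern.** The outcome ends on a calendar date; the tables end a fixed time after vaccination or discontinuation. The two agree only by coincidence. No other table in the SAP is specified on the outcome window: the wider set of unsolicited-AE tables in SAP 4.4 stops at the same Visit 4 or discontinuation limit.

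For subjects vaccinated early in the campaign, an SAE, AESI or NOCI can fall inside the primary window and still be absent from the tables that report it. The incidence shown would then not be the incidence as defined, and the length of the tabled window relative to the defined one would vary with the date of vaccination. The SAP has already accepted the principle at stake: its summary of changes says the unsolicited-AE cut-off was set to 22 days so that it matched the primary safety objective. The same alignment was not made for SAEs and NOCIs.

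**Working it through.** **Inputs**
- Second dose at Day 22 (+9): Protocol 7.2.1.
- Visit 4 at 180 ±14 days after the last dose, nominally Day 202: Protocol 7.4.
- Tables close 30 days after Visit 4 (completers): SAP 4.4.
- Passive surveillance ends on 15 May 2019 (cohort 1) and 15 May 2020 (cohort 2): Protocol 7.3 and 7.5, SAP 5.1.

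**The plan's own figure.** Day 22 + 180 = Day 202, as stated for Visit 4.

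**Table cut-off for a completer.** Second dose + 180 + 30 = second dose + 210 days. With Visit 4 at the early edge of its window it is 180 − 14 + 30 = 196 days; at the late edge, 180 + 14 + 30 = 224 days.

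**Second-dose date at which the cut-off equals 15 May**
- Cohort 1: 15 May 2019 − 210 days = 17 October 2018 (3 October at +14, 31 October at −14).
- Cohort 2: 15 May 2020 − 210 days = 18 October 2019 (4 October at +14, 1 November at −14).

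So a second dose before 3 October 2018 or 4 October 2019 always leaves some of the outcome window untabled, whatever the timing of Visit 4. One on or after 31 October 2018 or 1 November 2019 never does.

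**Illustrations.** The documents give no vaccination dates; the second-dose dates below are assumed. Untabled days = 15 May − cut-off, with the range over the ±14-day Visit 4 window.

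| Assumed second dose | Cohort 1 (2018-2019): cut-off; untabled days | Cohort 2 (2019-2020): cut-off; untabled days |
|---|---|---|
| 1 September | 30 March; 46 (32 to 60) | 29 March; 47 (33 to 61) |
| 15 September | 13 April; 32 (18 to 46) | 12 April; 33 (19 to 47) |
| 1 October | 29 April; 16 (2 to 30) | 28 April; 17 (3 to 31) |
| 15 October | 13 May; 2 (none to 16) | 12 May; 3 (none to 17) |
| 1 November | 30 May; none | 29 May; none |

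An end date later than 15 May, if instructed under Protocol 7.3, would add to the untabled days. A subject who received only one dose and stayed in the study has Visit 4 counted from that dose, so the cut-off is first dose + 210 days and comes earlier still.

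**The case against.** **No event is hidden.** A reader might infer that in-window events disappear from the report. They do not: SAP 4.4 lists them separately, and the appendix plans full SAE and NOCI listings. Protocol 11.5.2 asks only for listings of SAEs, so on SAEs the SAP already goes further than the protocol. This stands. What remains is that a listing gives no by-group counts, percentages or exact intervals, which is how SAP 4.4 chose to report these outcomes. The point weighs most for non-serious NOCIs, a primary outcome to which the protocol's sentence on SAE listings does not apply.

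**A 1 September second dose is not documented.** Protocol Table 3 starts cohort 1 swabs on 15 September 2018 and SAP 5.1 starts season 2 passive surveillance on 15 September 2019; 14 days earlier is 1 September in each case. But neither document derives 15 September from a dosing date, and the protocol's amendment history uses it as a calendar start for surveillance. The Kaplan-Meier axis in SAP 5.4.2, which runs to 240 days from Day 14 after the second dose, is compatible with doses in early September, but an axis is not a record of dosing. This objection stands: 46 and 47 days are illustrations, and if second doses began in mid-October the nominal loss would be 0 to 3 days.

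**Visit 4 is the last scheduled safety contact.** Later events reach the site through spontaneous report or contact about an influenza-like illness. A cut-off tied to the dose gives completers a similar observed period after vaccination, whereas a calendar cut-off adds less well ascertained time that varies with dose date. This is a fair reason to keep the present tables and to annotate the new ones. It does not make the present tables a report of the outcome as defined.

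**There is little inferential consequence.** No hypothesis test uses these outcomes, and vaccine-related SAEs are a subset of all SAEs. Both are true, and they limit the weight of the point.

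**Conclusion.** The point holds as a mismatch between outcome definition and tables. For completers with a second dose before 17 October 2018 or 18 October 2019 at nominal Visit 4 timing, the SAE, AESI and NOCI tables close before the primary window does. The date arithmetic is certain given the stated windows and a 15 May end. The effect on the results is not: it depends on vaccination dates that neither document gives, and it could be small.

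Two stronger readings are not supported:
- **Bias between arms.** Randomization is 1:1, stratified by cohort and age, and the cut-off rule is the same in both arms, so no difference in untabled time is expected.
- **A material overrun for late doses.** For second doses after the break-even date the cut-off does pass 15 May (by 15 or 14 days for 1 November at nominal timing). But SAEs and NOCIs are collected only to the end of participation (Protocol 7.3, 9.3). For cohort 1 that is 15 May at the latest, apart from ongoing follow-up (Protocol 7.5). SAEs after completion need not be reported unless the investigator suspects the product or a procedure (Protocol 9.3). That extra time can add few events.

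The change should be made because it concerns primary outcomes and is cheap, not because a large distortion has been shown.

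**What to change.** In SAP 4.4, run the primary SAE, AESI and NOCI tables on all reported events with onset from first vaccination to the end of passive surveillance as actually applied: 15 May, or the date instructed under Protocol 7.3. Include events reported after discontinuation when onset is inside that window. Capping the tables at the end of participation would drop vaccine-related SAEs reported after early termination, which Protocol 9.3 still asks for and SAP 3.1 counts.

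Keep the tables limited to 30 days after Visit 4 or discontinuation as supplementary, so that nothing now tabled is lost. Add a footnote to the primary tables that no safety contact is scheduled after Visit 4.

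The cost is a change of SAP wording, a date filter on data already collected, and one extra set of tables. Study conduct does not change.

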11.5.2. Analysis of Safety Data

Summaries and analysis of safety data will be presented for the Safety Analysis Population.

Solicited events will be summarized by severity for each day after each study vaccination (Days 0-7 post each study vaccination, 8 days in total) and as the maximum severity over all 8 days (day of the vaccination inclusive). Additionally, solicited events will be analyzed by taking the most severe response over the follow-up period and using standard techniques, such as exact confidence intervals, to summarize the proportion of subjects reporting each symptom, any injection site symptom, and any systemic symptom. Summaries of solicited events will be presented separately for each study vaccination as well as overall study vaccinations by treatment arm. The proportion of subjects reporting symptoms may be compared between treatment arms using Chi-square or Fisher's exact test, as appropriate. The proportion of subjects reporting solicited symptoms between the different study vaccinations (e.g., dose 1 vs. dose 2) will be compared using McNemar's test.

Unsolicited AEs will be coded by Medical Dictionary for Regulatory Activities (MedDRA[®]) for preferred term and system organ class (SOC). The number of SAEs is expected to be small in this trial and SAEs will be reported by detailed listings showing the event description, MedDRA[®] preferred term and SOC, relevant dates (study vaccinations and AEs), severity, relatedness, and outcome for each event. Non-serious unsolicited AEs will be summarized as number and percentage of subjects reporting at least one event in each MedDRA[®] preferred term and SOC, cross tabulated by severity and relationship to study product. Additionally, the proportion of subjects and exact 95% confidence intervals of AEs in aggregate and by MedDRA[®] categories will be computed.

Graphical presentations may include box plots and shift plots.

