## 1. INTRODUCTION

This study compares the safety and clinical efficacy of M-001, an influenza vaccine administered intramuscularly twice in older adults and the elderly ( $\geq 50$  years of age) versus placebo.

The M-001 vaccine is produced as a recombinant protein in *E. coli*. In the current study, the vaccine is intended to be administered in a non-adjuvanted formulation at a 1 mg/dose level that has been found to be safe and immunogenic in previous clinical trials performed by BiondVax.

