The percentage of subjects with any local or systemic reactogenicity solicited events overall and by vaccination will be compared between the groups using the chi-square test. Within-group comparison between the percentage of subjects with any local or systemic reactogenicity solicited events after first and second vaccination will be performed using Mc Nemar test.

Descriptive tables for duration of event will also be provided by solicited event.

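### SAP 4.4 prespecifies no between-arm estimate for SAEs, NOCIs or unsolicited AEs, although all three are primary safety outcomes

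*SAP*

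**What the plan says.** SAP section 3.1 puts all SAEs, related or not, among the primary safety outcomes, together with this item: "Occurrence of NOCIs from the time of the first study vaccination (M-001 or placebo) until end of the passive surveillance period". Vaccine-related SAEs and unsolicited AEs within 22 days of each vaccination are on the same list. Protocol section 3.2.1 gives them the same status. The SAP introduction states the purpose as a comparison with placebo: "This study compares the safety and clinical efficacy of M-001, an influenza vaccine administered intramuscularly twice in older adults and the elderly".

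The planned analysis is descriptive. Protocol section 11.5.2 says "The number of SAEs is expected to be small in this trial and SAEs will be reported by detailed listings". SAP section 4.4 goes further for SAEs, with by-arm counts and percentages and an interval: "Within group 95% CI for the proportion of subjects with serious SAEs will be derived using the exact method by SOC, PT". Table 14.2.13.8 matches this. For NOCIs it says "The number and percentage of subjects who experience one or more NOCIs will be tabulated by group", and Tables 14.2.14.1 to 14.2.14.4 carry no interval. For unsolicited AEs, exact intervals by SOC and PT appear in the SAP's overview of changes and in Tables 14.2.17.2 and 14.2.17.9.

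Elsewhere in section 4.4 the arms are compared directly. The percentage of subjects with any solicited reaction "will be compared between the groups using the chi-square test", and recorded temperature is treated the same way.

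**The concern.** Solicited reactions get a prespecified between-arm comparison, while the outcomes of most consequence for a benefit-risk judgement get none. The trial enrols about 12,000 people 1:1 and names these outcomes as primary. Its report should be able to say how large an excess of serious events or new chronic illness the data are compatible with. An interval around each arm's own proportion does not say that, and NOCIs lack even that interval.

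A comparison worked out later from the tables would have its estimator, stratification and choice of outcome rows settled after unblinding.

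**Working it through.** **1. The plan's own figures.** The only sample-size calculation for a comparison of arms concerns efficacy: 182 cases for 80% power at a true VE of 62% against 40%. With 1:1 allocation the vaccine share of cases is 0.6/1.6 = 0.375 under the null and 0.38/1.38 = 0.2754 under the alternative. With 182 cases, success requires at most 55 in the vaccine arm, and exact power is 81.5%. The figure reproduces, but it says nothing about SAEs or NOCIs. Neither document states a rate, precision or power for them.

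**2. Planned analyses side by side.**

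| Outcome | Status | Within-arm interval in SAP | Between-arm analysis in SAP |
|---|---|---|---|
| Any solicited reaction; temperature | primary safety | not specified | chi-square (4.4) |
| Subjects with ILI | secondary efficacy | stratified Wilson | stratified Newcombe difference with 95% CI (5.4.2) |
| Serious ILI, ILI hospitalisation, ILI death | exploratory efficacy, PP set | exact | Fisher's exact test (5.4.2) |
| SAEs | primary safety | exact, by SOC and PT | none |
| Unsolicited AEs | primary safety | exact, by SOC and PT | none |
| NOCIs | primary safety | none | none |

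**3. What a risk difference would deliver.** Inputs: n = 6,000 per arm (protocol section 4; the cohort figures give 2,027 + 4,000 = 6,027 and 2,028 + 4,000 = 6,028), and an assumed SAE proportion p, equal in both arms, of 1% to 3%. The protocol says only that SAEs should be few, so p is an assumption.

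Half-width = 1.96 × √(2p(1 − p)/n)

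- p = 1%: 1.96 × √(2 × 0.01 × 0.99/6,000) = 0.36 points
- p = 2%: 1.96 × √(2 × 0.02 × 0.98/6,000) = 0.50 points
- p = 3%: 1.96 × √(2 × 0.03 × 0.97/6,000) = 0.61 points

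Newcombe intervals give the same values to two decimals. With 60, 121 and 181 affected subjects in each arm (6,027 v 6,028), the corresponding 95% intervals for the risk ratio are 0.70 to 1.43, 0.78 to 1.28 and 0.82 to 1.23. No separate NOCI rate is assumed; the same formula applies at whatever proportion is seen.

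**4. Why within-arm intervals do not carry this information.** Suppose 121 of 6,028 placebo subjects (2.01%) and 168 of 6,027 M-001 subjects (2.79%) had an SAE. The exact within-arm intervals are 1.67% to 2.39% and 2.39% to 3.23%, and they just overlap. The difference is 2.79 − 2.01 = 0.78 points, with a Newcombe 95% CI of 0.23 to 1.33. The first pair of intervals conveys neither the size of the excess nor its uncertainty. This is an illustration for any SAE; the within-arm intervals that the SAP plans are at SOC and PT level.

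**The case against.** The descriptive plan fits the stated objectives. Safety is to be assessed by occurrence, the only hypothesis concerns VE, and the protocol promises SAE listings, which the SAP already exceeds. No document undertakes to give a between-arm SAE or NOCI estimate, so there is no contradiction between documents. All of that stands, and it makes this a recommendation rather than an error.

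Two other defences carry less weight. SAP section 10.1.1 has a general rule on intervals for treatment differences, but it governs presentation and assigns no estimate to SAEs or NOCIs. The DSMB may see safety data by arm, but that is not a reported estimate.

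A reader might infer more than the documents support:

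- *That the randomised comparison is thrown away, or that the trial could not state an excess.* Numbers and percentages are tabulated by arm, overall, by season and by age category, so a crude difference can be calculated. What is missing is a prespecified estimate. The Safety Population is also analysed by vaccine actually received at visit 1, so the contrast is as-treated and equals the randomised one only without allocation errors.
- *That safety is to be judged by whether the two arms' intervals overlap.* No section sets such a rule, and the planned SAE intervals are by SOC and PT, not for any SAE.
- *That arms are compared only for solicited reactions and temperature.* The Fisher tests for serious ILI, ILI hospitalisation and ILI death also touch serious events. They are exploratory efficacy analyses in the PP set and do not cover SAEs overall or NOCIs.
- *That the within-arm intervals should go.* Protocol section 11.5.2 asks for exact intervals for AEs in aggregate and by MedDRA category.

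**Conclusion.** The point holds as a gap in estimation. SAEs, NOCIs and unsolicited AEs are primary safety outcomes, and the SAP plans no between-arm estimate for them, with no interval of any kind for NOCIs. No planned result is invalid because of it. At an assumed SAE risk of 1% to 3% in both arms and 6,000 subjects per arm, the omitted estimate would have a 95% half-width of about 0.36 to 0.61 percentage points, or 3.6 to 6.1 per 1,000. The finding that no such estimate is planned rests on no assumed rate; only this illustration of size does. The change is worth making because it is cheap and fixes the method in advance.

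**What to change.** Amend SAP section 4.4 before unblinding. Keep the within-arm exact intervals. Add to the summary tables the risk difference, M-001 minus placebo, with a 95% CI, for four rows: any SAE, any vaccine-related SAE, any NOCI, and any unsolicited AE within the 22-day cut-off. Use the stratified Newcombe method of section 5.4.2, with strata formed by cohort and age group. Where counts are too sparse for four strata, use an unstratified Newcombe or exact interval. Vaccine-related SAEs are the likely case, since protocol section 2.3.1 reports no treatment-related SAEs to date. Label the rows as estimation in the as-treated Safety Population, with no hypothesis test and so no multiplicity adjustment.

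The cost is a few extra rows, using a method the SAP already requires and no new data. The downside is that sparse rows will have wide intervals.
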